#### 14.1.2 Visit [REDACTED]: Blood donation

In case it is not possible to perform the visit at the study site directly before the blood donation, e.g. if the BDU is located at another facility, the respective visit at the study site may be performed on the day before the blood donation.

- Vital signs
- Urinary pregnancy test in women of childbearing potential
- Eligibility for blood donation according to local law, including blood count, hemoglobin and infectious disease screen
  - Sample for analysis may be taken from the blood donation itself, or a separate blood sample taken prior to blood donation according to local regulations
  - However, the minimum panel to be tested is Anti-HIV-1/2, HBsAg, Anti-HBc, Anti-HCV and screening for syphilis
  - For Switzerland blood needs additionally to be tested for HTLV-1/2
- **Blood donation for IMP/Placebo production**
- MS relapse assessment
- Concomitant medication
- Adverse events

#### 14.1.3 Visits [REDACTED] IMP administration

- Vital signs will be recorded: within 15 min pre-dose, 15 min after Infusion start, Infusion end, 1h and 2h post-dose
- Urinary pregnancy test in women of childbearing potential
- **IMP/Placebo (see section 10.2.1):** A bedside test for blood group or cross-matching procedures will be performed according to local regulations and prior to each infusion.
- MS relapse assessment
- Concomitant medication
- Adverse events (**a telephone-based assessment of AEs will be done on the next working day after IMP administration.** If the phone consultation of the [REDACTED] coincides with the phone visit [REDACTED], the phone consultation of the [REDACTED] will be skipped.)\*

*\* In the Czech Republic, AEs will be recorded on the day after visit 3 and visit 4, as patients will be observed of 24 hours in the hospital.*

#### 14.1.4 Visit [REDACTED] Safety assessments

- Physical examination
- Vital signs
- MS relapse assessment
- Concomitant medication
- Adverse events

#### 14.1.5 Visit [REDACTED] [REDACTED] [REDACTED] [REDACTED] [REDACTED] [REDACTED] [REDACTED] End of Treatment (EOT)/ Early Discontinuation (ED) visit

- Physical examination
- Vital signs
- Urinary pregnancy test
- Hematology: complete blood count with differential and platelet count, Coombs test, coagulation studies (PT, PTT, INR) and sedimentation rate
- Clinical chemistry: Sodium, potassium, creatinine, eGFR, urea, total bilirubin, GGT, ALT/GPT, AST/GOT, alkaline phosphatase, total protein, albumin, lactate dehydrogenase, fibrinogen, CRP, iron, ferritin, haptoglobin
- Urinalysis: specific gravity, pH, glucose, protein, ketones, nitrite, leukocytes and blood
- Antigen specificity: collect only 10 ml EDTA blood [REDACTED] and 30 ml EDTA blood [REDACTED]
- Biomarker: collect one serum tube (5 ml)
- **Cranial MRI (contrast enhanced)**; (can be performed +/- 5 days of the visit. If the MRI will be performed before [REDACTED], urinary pregnancy test has to be performed at the site prior to the MRI.
- EDSS
- 9-HPT
- T25-FW
- SDMT
- MS relapse assessment
- Concomitant medication
- Adverse events

#### 14.1.6 Visit [REDACTED] [REDACTED] [REDACTED] Telephone interviews

\*A telephone interview will be conducted 3-5 days after the first dose of study drug has been administered. The purpose of this interview is to identify and collect information on changes in the patient's health status that warrant an unscheduled visit (e.g., new or worsening neurological symptoms). During the telephone interview, patients will be asked questions related to potential adverse events (AEs) or if they noticed any change in neurological functions. Concomitant medications will be recorded. The telephone interview will be conducted by the principal

investigator or a delegate from the study team. All clinically significant findings will be reported in the appropriate eCRF.

#### 14.1.7 Visit [REDACTED] Safety Follow Up

- Physical examination
- Vital signs
- Urinary pregnancy test in women of childbearing potential
- Hematology: complete blood count with differential and platelet count, Coombs test, coagulation studies (PT, PTT, INR) and sedimentation rate
- Clinical chemistry: Sodium, potassium, creatinine, eGFR, urea, total bilirubin, GGT, ALT/GPT, AST/GOT, alkaline phosphatase, total protein, albumin, lactate dehydrogenase, fibrinogen, CRP, iron, ferritin, haptoglobin
- Urinalysis: specific gravity, pH, glucose, protein, ketones, nitrite, leukocytes and blood
- **Cranial MRI (without contrast)**; can be performed +/- 5 days of the [REDACTED] and up to 5 days before [REDACTED]. If the MRI will be performed before the respective visit, urinary pregnancy test has to be performed at the site prior to the MRI.
- EDSS
- 9-HPT
- T25-FW
- SDMT
- MS relapse assessment
- Concomitant medication
- Adverse events

#### 14.1.8 Unscheduled Visit

In case of symptoms that suggest a possible relapse, i.e. new neurological symptoms or worsening of previous symptoms, the following assessments will be performed during an unscheduled visit:

- Physical examination
- Vital signs
- Urinary pregnancy test in women of childbearing potential
- **Cranial MRI (without contrast)**; (can be performed  $\pm 5$  days). If the MRI will be performed before the UV urinary pregnancy test has to be performed at the site prior to the MRI
- Hematology: complete blood count with differential and platelet count, Coombs test, coagulation studies (PT, PTT, INR) and sedimentation rate
- Clinical chemistry: Sodium, potassium, creatinine, eGFR, urea, total bilirubin, GGT, ALT/GPT, AST/GOT, alkaline phosphatase, total protein, albumin, lactate dehydrogenase, fibrinogen, CRP, iron, ferritin, haptoglobin
- Urinalysis: specific gravity, pH, glucose, protein, ketones, nitrite, leukocytes and blood
- EDSS
- 9-HPT, T25-FW, SDMT

- MS relapse assessment
- Concomitant medication
- Adverse events
- In case of symptoms not related to a potential relapse, it is up to the Investigator to decide which of the abovementioned assessments should be performed during the unscheduled visit.

#### 14.1.9 Last Visit in Patients who Prematurely Discontinue the Study (ED Visit)

Patients who received at least one dose of study drug and prematurely discontinue the treatment period will be investigated immediately (but not earlier than 2 weeks after the last dose) according to the premature discontinuation visit (ED). This will also apply to patients who have prematurely discontinued the safety follow-up phase and whose last visit has been more than 8 weeks ago.

At the ED visit an MRI needs to be performed unless a previous MRI had been performed less than 2 weeks prior to the ED visit. The MRI at the ED visit needs to be with contrast.

#### 14.1.10 Re-screening of patients

A patient may be re-screened once if any inclusion criterion is not met, or any exclusion criterion is met during the first screening attempt. In case of re-screening, all parameters which have already been assessed during initial screening with the exception of HLA typing must be reassessed.

Note: In case of narrowly missed safety laboratory values during screening as defined in Section 8.1.2 'exclusion criteria', repeat samples may be drawn once. This repetition of laboratory values is not regarded as re-screening.

#### 14.2 Tabular Overview of Treatment Schedule

A tabular summary of the treatment schedule and assessments in this study is given in the study synopsis at the beginning of the clinical study protocol.

#### 14.3 Windows for Scheduled Visits

Baseline visit (visit 1) of the patients will be scheduled to review inclusion and exclusion criteria. Time point of [REDACTED] blood donation start of the IMP administration will be coordinated centrally to ensure appropriate safety assessments between dosing of patients. [REDACTED]

Due to organizational reasons, the study design and the manufacturing schedule, the treatments could be postponed as well. However, both treatments of one cycle will be administered [REDACTED]

All safety visits will be planned and performed based on the previous visit, e.g. if there is a postponement of one week, the following visit will also be postponed at least by one week.

It is ensured that there is [REDACTED] between the two blood donations.

#### 14.4 Assessment of Compliance

Patients are expected to maintain compliance with the visit schedule within the permitted study visit windows. Site staff must have regular contact with each patient throughout the study to ensure that contact information is correct and to remind them of upcoming visits.

#### 14.5 Special Warnings and Precautionary Measures

**Allergic/anaphylactic and other infusion-related reactions:** As a precautionary measure, patients must be kept under medical supervision for at least 2 hours following IMP/placebo administration during the first treatment cycle to allow for an adequate observation and adequate treatment in case of potential allergic or other infusion related reactions. During the second treatment cycle the observation period is 1h following IMP administration. Furthermore, during the first treatment cycle, a telephone-based assessment of AEs will be done the day after IMP/placebo administration. In case of severe allergic (anaphylactic) reactions, standardized medical treatment should be applied. An example for an emergency treatment is given in the Appendix 24.2.

**Infection:** Some biologic and non-biologic therapies for the treatment of MS have been associated with an increased risk of infection. As a measure of precaution, the Investigator or Study Physicians are required to carefully monitor for any signs or symptoms of infection such as, but not limited to, increased body temperature, malaise, sweats, cough, dyspnea etc.

A **Data and Safety Monitoring Board (DSMB)** has been established to assess safety of patients treated in the study (for details on DSMB responsibilities see section 19.1.3).

**Investigators** are instructed not to proceed with the next IMP infusion if:

- the study participant is pregnant
- the study participant experienced allergic reaction in prior IMP administration
- the study participant experienced a severe infusion-related reaction in prior IMP administration
- the study participant experienced a serious AR to prior IMP administration
- the study participant experiences an SAE at the time of IMP infusion or any other serious medical condition, which poses a threat to the safety of IMP administration
- the Sponsor or Steering Committee or DSMB have decided to not continue IMP administration in the trial arm concerned

In case of questions or uncertainties regarding IMP administration following adverse events, the Investigator should contact the medical monitor (primary contact) or the Sponsor's Medical Representative. Contact details are given at the beginning of the study protocol.

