## 4 SCHEDULE OF EVENTS AND TREATMENT

### 4.1 Part A

Visit																UV
																Unscheduled 
Week																
Study Phase	BL	Treatment												SFU		
Informed consent	x															
Eligibility criteria	x	x														
Body weight, height	x															
ECG	x															
Medical history including MS history  / Demography/ Smoking history/ Prior medication/ SARS-CoV-2 vaccination status	x															
Physical examination	x					x	x						x		x	x
Vital signs	x	x	x	x		x	x		x	x	x		x		x	x
Urine pregnancy test 	x	x	x	x			x		x	x	x		x		x	x
HLA typing 	x															
Cranial MRI	x 						x 						x 		x 	x 
Hematology  / Blood biochemistry 	x						x						x		x	x
Urinalysis 	x						x						x		x	x
Infectious disease screen 	x															
EDSS	x						x						x		x	x
9-HPT, T25-FW, SDMT	x						x						x		x	x
Eligibility for blood donation 																
Blood donation																

Visit																	UV
																	Unscheduled 
Week																	
Study Phase	BL	Treatment												SFU			
CLS12311/ (Placebo) 																	
Concomitant medication/procedures		x	x	x	x	x	x	x	x	x	x	x	x	x	x	x	x
MS relapse assessment		x	x	x		x	x		x	x	x		x		x	x	x
Adverse event assessment	x	x	x	x	x	x	x	x	x	x	x	x	x	x	x	x	x
Telephone-based AE assessment the next day following infusion 			x	x						x	x						
Antigen specificity 	x						x						x				
Biomarker blood	x						x						x				

MS Multiple Sclerosis; MRI Magnetic Resonance Imaging; EDSS Expanded Disability Status Scale (neurological rating scale); 9-HPT Nine Hole Peg Test (clinical test for hand function); T25-FW Timed 25-Foot Walk; SDMT Symbol Digit Modalities Test (cognitive test); ECG electrocardiogram; BL Baseline; EOT End of Treatment; EOS End of Study; ED Early Discontinuation; SFU Safety Follow Up; HLA Human Leukocyte Antigen

 MS history means first MS symptoms and diagnosis, prior relapses, prior disease modifying therapies and symptomatic therapies.

 Only in female patients of childbearing potential (sexually mature, premenopausal and not surgically sterile). To be performed locally.

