### 10.2.3 Method of Administration

Study treatment will be administered on an outpatient basis. The product bag(s) should be taken out from the fridge or cooling box approx. 30 min prior to the application. A bedside test for blood group or cross-matching procedures will be performed according to local regulations and prior to infusion. The administration of CLS12311/placebo is performed by i.v. infusion of the entire product bags over a 30 to 60-minute period using a standard blood component kit with inline filter (40 µm). The infusion should typically run with 5 ml/min, corresponding to approx. 1.7 drops per second. Standard study site guidelines will be followed to ensure sterility of the material and appropriate methods for intravenous administration.

The Investigator or his representative will document the time and volume of CLS12311/placebo administration for each patient. For incomplete volume administration (e.g. discontinuation due to AE), the reasons must be documented.

CLS12311 (or placebo) infusions should be initiated and supervised by an experienced professional with access to appropriate medical support to manage severe reactions (see Appendix 24.2).

All patients will be observed at the clinical site for at least 2 hours after the completion of the administration of the CLS12311/placebo. After completion of the infusion, the i.v. cannula should remain in situ for at least 2 hours to allow for administration of drugs intravenously, if necessary, in the event of a delayed reaction. If no adverse event occurs during this period of time, the i.v. cannula may be removed, and the patient may be discharged\*.

AEs during administration and observation must be documented according to the procedures outlined in section 13.

*\* In Czech Republic, all patients will be admitted as inpatients and will be observed for 24 hours following administration of CLS12311.*

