### **13.4 Potential Risks and Potential Adverse Events**

The risk to patients in this trial will be minimized by compliance with inclusion/exclusion criteria, close clinical and imaging monitoring during the study, assessment of the nature, frequency, and severity of adverse events, avoidance of prohibited treatments and adherence to Investigator guidance. In addition, guidelines for managing severe allergic reactions are provided in the Appendix 24.2. Detailed criteria for study discontinuation are given in section 9.3 and post-treatment observational periods defined in sections 10.2.3 and 14.5. Furthermore, safety will be closely monitored on an ongoing basis by a Data and Safety Monitoring Board (DSMB) as outlined in section 19.1.3.

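### Protocol 14.5 sets 1 h of observation after second-cycle infusions, but 10.2.3 requires at least 2 h and a 2-h vital-sign reading is scheduled at the same visits

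*Protocol*

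**What the plan says.** Protocol 14.5 asks for at least 2 h of medical supervision after infusions in the first cycle. It then says: "During the second treatment cycle the observation period is 1h following IMP administration". On the follow-up call it says only that "during the first treatment cycle, a telephone-based assessment of AEs will be done the day after IMP/placebo administration", and it is silent about calls in the second cycle.

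Other parts of the plan differ:

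- Protocol 10.2.3: "All patients will be observed at the clinical site for at least 2 hours after the completion of the administration of the CLS12311/placebo". The cannula must also stay in for at least 2 h, and discharge follows if that time passes without an adverse event. The only local variation is a longer one: "In Czech Republic, all patients will be admitted as inpatients and will be observed for 24 hours following administration of CLS12311".
- Protocol 14.1.3, on the infusion visits, lists vital signs before dosing and then "15 min after Infusion start, Infusion end, 1h and 2h post-dose". It adds that "a telephone-based assessment of AEs will be done on the next working day after IMP administration".
- The schedule in Protocol 4.1 has a row headed "Telephone-based AE assessment the next day following infusion", marked at four visits.
- SAP 5.5.9 names Visits 3, 4, 10 and 11 for timed vital signs. The last reading falls 2 h after the end of the second bag.
- Protocol 13.4 refers the reader to "post-treatment observational periods defined in sections 10.2.3 and 14.5" and does not say which section prevails.

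**The concern.** The two sections named as defining the observation period give different answers for the second cycle. A site that works from 14.5 could send a re-dosed patient home at 1 h, before the 2-h vital signs are due, and might not make the next-day call. Section 14.5 does not forbid the call, so its loss is possible rather than prescribed.

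This matters because the safety of a second cycle is a stated aim (Protocol 5.2.3 and 7.1) in a first-in-human trial. Section 5.2.3 expects acute reactions such as cytokine release or thrombosis in the first hours after treatment. The AESI definition in 12.1.1.1 covers the treatment day and the day after, which is the window the call serves.

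The SAP also separates the cycles. Its crude adverse-event tables are presented by study period (5.5.1, with periods defined in 4.6), and Table 15.2.9 reports vital signs by visit and time point. With 1, 2 and 3 re-dosed patients in the low, medium and high dose groups, one site's practice can decide a row.

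**Working it through.** The plan gives no figure to reproduce, so the check sets the texts side by side and then bounds the exposure.

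**Which visits are second-cycle infusions.** The visit numbers in the heading of 14.1.3 are blacked out. SAP 5.5.9 names Visits 3, 4, 10 and 11 for the peri-infusion readings. Protocol Table 12-1 places the donation-related infectious disease screen at Visits 1/2 and again at Visit 9, so Visits 10 and 11 follow the second donation. In the schedule row for the next-day call, the marks stand in columns 3, 4, 10 and 11 by position.

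**What each text requires in the second cycle.**

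| Item | 14.5 | Elsewhere |
|---|---|---|
| Observation after infusion | 1 h | at least 2 h, all patients (10.2.3) |
| Cannula in place | not stated | at least 2 h (10.2.3) |
| Last vital-sign reading | not stated | 2 h after second bag, Visits 10 and 11 (SAP 5.5.9) |
| Next-day call | mentioned for first cycle only | marked at Visits 10 and 11 (schedule 4.1) |

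The gap is at least 60 min of supervision, and a patient discharged at 1 h misses the 2-h reading.

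**Infusion days exposed (upper bound).** Inputs are 6 patients in the second cycle (synopsis), two treatment days per cycle (5.2.2) and group sizes of 1, 2 and 3 (7.1).

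- All infusion days: 6 × 2 = 12.
- Days that include CLS12311: group 1 has one, because its second treatment day is placebo only (10.2.1). The total is 1 × 1 + 2 × 2 + 3 × 2 = 11.

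**Time on site from start of infusion.** Inputs are two 150 ml bags and a typical rate of 5 ml/min (10.2.3).

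- Infusion time: 2 × 150 / 5 = 60 min.
- With 2 h of observation: 60 + 120 = 180 min. With 1 h: 60 + 60 = 120 min.
- Reduction: (180 − 120) / 180 = 33%.
- If the infusion takes 30 min: 150 against 90 min, a 40% reduction.
- If it takes 120 min (60 min per bag): 240 against 180 min, a 25% reduction.

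The post-infusion supervision itself halves, from 2 h to 1 h, whatever the infusion time.

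**Calls at stake.** The rule for skipping a call that coincides with a phone visit has its visit numbers blacked out. If it never applies in the second cycle, 6 × 2 = 12 calls are at stake. If it removes every Visit 11 call, 6 are.

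**The case against.** The strongest reply is that 10.2.3 contains the explicit discharge rule and 14.5 does not mention discharge. Read together they give at least 2 h, so early discharge would breach 10.2.3. A careful site can satisfy every section by keeping patients 2 h and making the call. This is true, and no early discharge is documented. But 14.5 states its shorter period as a rule, and 13.4 gives it equal standing.

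A second reply is that a shorter stay after a tolerated first cycle may be deliberate, especially since 14.5 bars re-infusion after an allergic or severe infusion-related reaction. If so, 10.2.3 and SAP 5.5.9 are wrong for the second cycle, and text must still change. No reason for shortening is given.

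Several limits on the size of the effect stand:

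- Section 14.1.3 alone cannot show second-cycle scope. Its visit numbers are blacked out and its Czech note names only Visits 3 and 4. The scope rests on SAP 5.5.9 and column position in the schedule.
- The 25% to 40% range adds little to the plain halving of supervision. A 30-min infusion of both bags needs 10 ml/min, twice the typical rate.
- Adverse events are collected at later visits and can be reported by patients.
- Missing readings would show in the counts of Table 15.2.9 and could be traced through Listings 16.2.2.2 and 16.2.11, although no planned table would give the reason.
- The SAP was finalised after a data review, so an amendment may come too late to protect anyone.

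**Conclusion.** The conflict is real and should be fixed. For the second cycle, 14.5 gives 1 h where 10.2.3 gives at least 2 h and SAP 5.5.9 schedules a reading at 2 h.

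At most 12 infusion days in 6 patients are affected, 11 of them with CLS12311, together with 6 to 12 next-day calls. These bounds assume that all planned second cycles are given and that every site follows 14.5 literally. Observation for 24 h at Czech sites lowers them by an unknown amount, because patient numbers by country are not given.

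The main cost is weaker supervision of re-dosed patients and 2-h readings whose absence the tables would not explain. The likely effect on adverse-event counts is small.

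**What to change.** Amend Protocol 14.5 so that at least 2 h of supervision and the next-working-day call apply in both cycles. Keep the skip rule, the Czech 24-h rule and the 2-h reading at Visits 10 and 11. If 1 h was intended, the alternative is an explicit, justified second-cycle exception in 10.2.3, 14.1.3 and SAP 5.5.9. The first route is simpler and adds no procedure that is not already scheduled.

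For infusions already given, derive observation time as discharge time minus infusion end time. Report it by cycle and dose group beside Table 15.1.11. Footnote Table 15.2.9 and the crude adverse-event tables by period wherever it was under 2 h.

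The cost is one or two sentences in 14.5, one derived row and a few footnotes in the SAP outputs. No new data are needed, because SAP 5.4 already lists application start and end times and the date and time of discharge.

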## 15 STUDY AND TREATMENT DURATION

### 15.1 Duration per Patient

The total duration of study participation for each subject will be at least 48 weeks. Subject eligibility will be determined at Baseline. Patients who meet all criteria for enrollment will be centrally allocated to the dose group. Hence, the timing of the visit 2 (1st blood donation) will depend on sequential allocation and respective safety periods defined between IMP administrations. Subsequently, a 17-week treatment phase begins, followed by a 31-week safety follow up phase.

